8.4. Data sources

Data for this study will originate from selected national registries in Denmark, Norway and Sweden. [Table 1](#) summarizes definition of exposures, outcomes along with the data sources that will be used to identify variables for this study. In each country, data from all registries are individually linkable via a unique personal identifier. An important advantage is similar data structure, and coding systems used in all three Scandinavian countries.

Table 1. National registries in Denmark, Norway and Sweden and type of data available from each

Variable	Role	Data source(s)	Operational definition
AF and inclusion/exclusion criteria based on hospital diagnoses and procedures	Definition of the study population	Danish National Patient Registry (30), Norwegian Patient Registry (41), Swedish National Patient Register (32, 42)	See Statistical analysis plan (SAP)
Initiation of an OAC (apixaban, dabigatran, rivaroxaban, warfarin)	Exposure	Danish National Health Services Prescription Database (33, 43), Norwegian Prescription Database (33), Swedish Prescribed Drug Register (33)	See SAP
Any stroke/systemic embolism	Endpoint	Danish National Patient Registry (30), Norwegian Patient Registry (41), Swedish National Patient Register (32, 42)	See SAP

ELIQUIS® (apixaban)
B0661103 NON-INTERVENTIONAL STUDY PROTOCOL
Amended, 05 JULY, 2018

Variable	Role	Data source(s)	Operational definition
Ischaemic stroke	Endpoint	Danish National Patient Registry (30), Norwegian Patient Registry (41), Swedish National Patient Register (32, 42)	See SAP
Haemorrhagic stroke	Endpoint	Danish National Patient Registry (30), Norwegian Patient Registry (41), Swedish National Patient Register (32, 42)	See SAP
All bleeding outcomes	Endpoint	Danish National Patient Registry(30), Norwegian Patient Registry(41), Swedish National Patient Register (32, 42)	See SAP
Intracranial bleeding	Endpoint	Danish National Patient Registry(30), Norwegian Patient Registry(41), Swedish National Patient Register (32, 42)	See SAP
Gastrointestinal bleeding	Endpoint	Danish National Patient Registry(30), Norwegian Patient Register(41), Swedish National Patient Register (32, 42)	See SAP
Other bleeding	Endpoint	Danish National Patient Registry (30), Norwegian Patient Registry (41), Swedish National Patient Register (32, 42)	See SAP
Acute myocardial infarction	Endpoint	Danish National Patient Registry (30), Norwegian Patient Registry (41), Swedish National Patient Register (32, 42)	See SAP
Death of all causes	Endpoint	Danish Civil Registration System (31), National Population Register of Norway, Swedish Total Population Register (29), National Registry (Norway) (44), Swedish Population Register (29)	See SAP
Any hospitalized bleeding	Endpoint	Danish National Patient Registry (30), Norwegian Patient Registry (41), Swedish National Patient Register (32, 42)	See SAP
Emigration	Censoring variable	Danish Civil Registration System (31), National Population Register of Norway, Swedish Total Population Register (29), National Registry (Norway) (44), Swedish Population Register (29)	See SAP
Sex	Covariate	Danish Civil Registration System (31), National Population Register of Norway, Swedish Total Population Register (29), National Registry (Norway) (44), Swedish Population Register (29)	See SAP
Age, years	Covariate/subgroup variable	Danish Civil Registration System (31), National Population Register of Norway, Swedish Total Population Register (29), National Registry(Norway) (44), Swedish Population Register (29)	See SAP
CHA ₂ DS ₂ VASc score (45, 46)	Covariate/subgroup variable	Danish National Patient Registry (30), Norwegian Patient Registry (41), Swedish National Patient Register (32, 42) Danish National Health Services Prescription Database (33, 43), Norwegian Prescription Database (33), Swedish Prescribed Drug Register (33)	See SAP
CHADS ₂ score	Covariate/subgroup variable	Danish National Patient Registry (30), Norwegian Patient Registry (41), Swedish National Patient Register (32, 42) Danish National Health Services Prescription Database (33, 43), Norwegian Prescription Database (33), Swedish Prescribed Drug Register (33)	See SAP

Variable	Role	Data source(s)	Operational definition
HAS-BLED, score (45, 46)	Covariate/subgroup variable	Danish National Patient Registry (29), Norwegian Patient Registry (41), Swedish National Patient Register (31, 42) Danish National Health Services Prescription Database (33, 43), Norwegian Prescription Database (33), Swedish Prescribed Drug Register (33)	See SAP
Concomitant medication	Covariate	Danish National Health Services Prescription Database (33, 43), Norwegian Prescription Database (33), Swedish Prescribed Drug Register (33)	See SAP
Comorbidities	Covariates	Danish National Patient Registry (30), Norwegian Patient Registry (41), Swedish National Patient Register (32, 42)	See SAP
Health care utilisation	Descriptive characteristics	Danish National Patient Registry (30), Norwegian Patient Registry (41), Swedish National Patient Register (32, 42)	See SAP
Household income	Covariate	Statistics Denmark, Statistics Norway [not for pooled analysis], Statistics Sweden	See SAP
Education	Covariate	Statistics Denmark, Statistics Norway [not for pooled analysis], Statistics Sweden	See SAP
Employment	Covariate	Statistics Denmark, Statistics Norway [not for pooled analysis], Statistics Sweden	See SAP
Health care cost	Endpoint	Published data on health care costs for specific types of visit	See SAP

8.5. Study size

Table 2 shows the number of users of NOACs in Denmark, Norway and Sweden in 2013-2015. Population risk of major bleeding in the study population is 2-3% per year (47). The number of eligible OAC users with NVAF will be smaller. A recent Danish comparative effectiveness study of OACs in new users with NVAF based on OACs use data between 2012 and 2015 enrolled approximately 35,000 initiators of warfarin, 12,000 initiators of dabigatran (150 mg); 7,000 initiators of rivaroxaban (20 mg), and 6,000 initiators of apixaban (5 mg) (13). In the apixaban group there were 90 cases of major bleeding after 1 year of follow-up and 109 cases after 2.5 years of follow-up (13). Another Danish study included more than 50,000 NOAC initiators with NVAF in August 2011-February 2016, of whom 70% were VKA naïve; the study included more than 12,000 initiators each of apixaban and rivaroxaban and more than 25,000 initiators of dabigatran. The study also demonstrated that about half of the NOAC initiators use these medications for the AF indication (19). In Norway, a study of anticoagulant-naïve NVAF patients initiating warfarin or NOACs in 2013-mid 2015, there were more than 6,000 initiators each of apixaban and rivaroxaban and nearly 8,000 initiators of dabigatran (16). Conservatively assuming the size of the apixaban cohort to be 24,000 patients in 2015, the expected number of major bleeding events in the apixaban group (the smallest) is 300 – 400 in the first year of follow-up.

Table 2. Persons ages 20 years or older with a dispensing of NOACs and VKAs for any indication in Denmark, Norway and Sweden, 2013-2015*

ATC code (active substance)	Denmark			Norway			Sweden		
	2013	2014	2015	2013	2014	2015	2013	2014	2015

B01AE07 (Dabigatran etexilate)	21,617	23,465	21,212	13,873	15,351	13,835	10,658	13,627	14,013
B01AF01 (Rivaroxaban)	10,877	16,023	22,500	13,394	20,759	25,439	9,652	21,140	33,868
B01AF02 (Apixaban)	1,772	8,023	17,926	2,258	8,636	21,498	2,072	17,132	46,926
B01AA(VKAs)**	91,202	89,783	87,851	87,900	77,681	69,212	202,729	202,729	188,966

*Unique in each calendar year; age categories as reported by the sources listed below
 **Nearly all warfarin, e.g., in 2015 Denmark 98.2%, Norway 99.9%;Sweden 99.8%
 Sources:
 Denmark www.medstat.dk;
 Norway www.norpd.no;
 Sweden <http://www.socialstyrelsen.se/statistik/statistikdatabas/lakemedel%>

Table 3, Table 4, Figure 3 and Figure 4 show the per-group size needed to detect a given increase/reduction of 1-year bleeding risk for alpha = 0.025 and alpha = 0.05 (calculations performed using PROC POWER in SAS 9.4). The 1-year background risk of bleeding was set to 2% in Table 3, and 3% in Table 4. The estimations show that the study should be able to identify a relative risk (RR) of 0.8 with a power of 90% and an alpha of 0.05 in a population with a background yearly bleeding risk of 2% if there are included at least 17,307 apixaban users (the smallest group) (Table 3). The estimations furthermore show that the study should be able to identify a relative risk of 0.8 with a power of 90% and an alpha of 0.05 in a population with a background yearly bleeding risk of 3% if there are at least 11,433 apixaban users (the smallest group) (Table 4). Similar computations apply to the other primary endpoint of stroke/systemic embolism.

Table 3. Group size for pairwise estimation of RR for a NOAC vs. warfarin 0.8 to 1.5. Assumptions: alpha=0.025 or 0.05. 1-year background risk of bleeding = 0.02

Computed Number (N) per Group					
Index	Alpha	Relative Risk	Nominal Power	Actual Power	N per Group
1	0.025	0.8	0.8	0.800	20959
2	0.025	0.8	0.9	0.900	27367
3	0.025	0.9	0.8	0.800	88543
4	0.025	0.9	0.9	0.900	115614
5	0.025	1.1	0.8	0.800	97671
6	0.025	1.1	0.9	0.900	127534
7	0.025	1.2	0.8	0.800	25530
8	0.025	1.2	0.9	0.900	33335
9	0.025	1.3	0.8	0.800	11833
10	0.025	1.3	0.9	0.900	15451
11	0.025	1.4	0.8	0.800	6927
12	0.025	1.4	0.9	0.900	9044

Computed Number (N) per Group					
Index	Alpha	Relative Risk	Nominal Power	Actual Power	N per Group
13	0.025	1.5	0.8	0.800	4604
14	0.025	1.5	0.9	0.900	6011
15	0.050	0.8	0.8	0.800	17307
16	0.050	0.8	0.9	0.900	23170
17	0.050	0.9	0.8	0.800	73115
18	0.050	0.9	0.9	0.900	97880
19	0.050	1.1	0.8	0.800	80653
20	0.050	1.1	0.9	0.900	107972
21	0.050	1.2	0.8	0.800	21082
22	0.050	1.2	0.9	0.900	28222
23	0.050	1.3	0.8	0.800	9772
24	0.050	1.3	0.9	0.900	13081
25	0.050	1.4	0.8	0.800	5720
26	0.050	1.4	0.9	0.900	7657
27	0.050	1.5	0.8	0.800	3802
28	0.050	1.5	0.9	0.900	5089

Figure 3. Group size for pairwise estimation of RR for a NOAC vs. warfarin 0.8 to 1.5.
Assumptions: alpha=0.025 or 0.05. 1-year background risk of bleeding = 0.02

[figure not shown]
[figure not shown]

Table 4. Group size for pairwise estimation of RR for a NOAC vs. warfarin 0.8 to 1.5.
Assumptions: alpha=0.025 or 0.05. 1-year background risk of bleeding = 0.03

Computed N per Group					
Index	Alpha	Relative Risk	Nominal Power	Actual Power	N per Group
1	0.025	0.8	0.8	0.800	13845
2	0.025	0.8	0.9	0.900	18078
3	0.025	0.9	0.8	0.800	58457
4	0.025	0.9	0.9	0.900	76330
5	0.025	1.1	0.8	0.800	64416
6	0.025	1.1	0.9	0.900	84111
7	0.025	1.2	0.8	0.800	16829
8	0.025	1.2	0.9	0.900	21974
9	0.025	1.3	0.8	0.800	7797
10	0.025	1.3	0.9	0.900	10180
11	0.025	1.4	0.8	0.800	4561
12	0.025	1.4	0.9	0.900	5956
13	0.025	1.5	0.8	0.800	3030
14	0.025	1.5	0.9	0.900	3957
15	0.050	0.8	0.8	0.800	11433
16	0.050	0.8	0.9	0.900	15305
17	0.050	0.9	0.8	0.800	48272
18	0.050	0.9	0.9	0.900	64622
19	0.050	1.1	0.8	0.800	53192
20	0.050	1.1	0.9	0.900	71209
21	0.050	1.2	0.8	0.800	13897
22	0.050	1.2	0.9	0.900	18604
23	0.050	1.3	0.8	0.800	6438
24	0.050	1.3	0.9	0.900	8619
25	0.050	1.4	0.8	0.800	3767
26	0.050	1.4	0.9	0.900	5042
27	0.050	1.5	0.8	0.800	2502
28	0.050	1.5	0.9	0.900	3350

Figure 4. Group size for pairwise estimation of RR for a NOAC vs. warfarin 0.8 to 1.5.
Assumptions: alpha=0.025 or 0.05. 1-year background risk of bleeding = 0.03

[figure not shown]

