
peripheral arterial disease. The primary analyses will be conducted using all licensed NOAC doses. Sensitivity analyses for the primary and composite secondary endpoints will include those of reduced OAC doses, depending on sample size, intention-to-treat-like analyses, analyses using alternative covariate adjustment methods; and varying definitions of treatment variables and selected endpoints. *Study Size*: The study will include at least 11,000 patients who were dispensed apixaban for the first time during the study period. *Data analyses*: Data from the three countries will be combined on the individual level. Crude and adjusted hazard ratios will be computed, using pairwise contrasts of each NOAC against warfarin. Adjusted estimates will be obtained using NOAC-warfarin pairwise propensity-score matched samples. This study will provide real world evidence about safety and effectiveness of each NOAC compared with warfarin in patients with NVAF overall and in selected patient subgroups. *Milestones*: The data collection is anticipated to start on 1st October, 2017 and the Final Study Report will be submitted approximately end of December, 2018.

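### Protocol 8.5 claims 90% power for group sizes that its own Tables 3 and 4 list at 80%, and the abstract's minimum of 11,000 falls below both

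*Protocol*

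**What the plan says.** Section 8.5 introduces Tables 3 and 4 as the sizes per group "needed to detect a given increase/reduction of 1-year bleeding risk for alpha = 0.025 and alpha = 0.05". On the planning risks it says: "The 1-year background risk of bleeding was set to 2% in Table 3, and 3% in Table 4".

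It then draws two conclusions from the tables:

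- At 2% risk, the condition set is "if there are included at least 17,307 apixaban users (the smallest group) (Table 3"). The claim attached to that size, for a relative risk of 0.8, is detection "with a power of 90% and an alpha of 0.05 in a population with a background yearly bleeding risk of 2"%.
- At 3% risk, the condition set is "if there are at least 11,433 apixaban users (the smallest group) (Table 4"). The claim attached to that size, for the same relative risk, is detection "with a power of 90% and an alpha of 0.05 in a population with a background yearly bleeding risk of 3"%.

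It adds that similar calculations apply to the other primary endpoint, stroke or systemic embolism.

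The abstract gives the size commitment: "The study will include at least 11,000 patients who were dispensed apixaban for the first time during the study period". It attaches no power, relative risk or background risk to that number.

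**The concern.** The two sentences in 8.5 and the tables they cite cannot both be right. The text attaches 90% power to 17,307 and 11,433. In the tables both numbers stand in the row for 80%.

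This is the protocol's only power statement for the primary bleeding endpoint, and it is carried over to the other primary endpoint. Someone reading a null result against it would believe that the chance of missing a relative risk of 0.8 at those sizes was 10%, when the tables put it at 20%. The abstract's minimum is lower than either quoted size, so a study that only just met its commitment would be further still from 90%.

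**Working it through.** **Text against tables** (alpha 0.05, relative risk 0.8)

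| Background risk | Size in text | Power claimed in text | Table row holding that size | Power in that row | Table size for 90% |
|---|---|---|---|---|---|
| 2% | 17,307 | 90% | Table 3, index 15 | 0.8 nominal, 0.800 actual | 23,170 (index 16) |
| 3% | 11,433 | 90% | Table 4, index 15 | 0.8 nominal, 0.800 actual | 15,305 (index 16) |

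Ratios: 23,170 / 17,307 = 1.34 and 15,305 / 11,433 = 1.34.

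**Which of the two is right**

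Inputs from 8.5: p1 = 0.02 or 0.03, p2 = 0.8 × p1, alpha 0.05, equal groups. Sidedness is not stated, so two-sided was tried first. With p̄ = (p1 + p2)/2,

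n per group = [z(1−α/2)·√(2p̄(1−p̄)) + z(power)·√(p1(1−p1) + p2(1−p2))]² / (p1 − p2)²

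At 2%: p2 = 0.016, p̄ = 0.018, and the two square roots are 0.18802 and 0.18800.

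- 80%: (1.95996 × 0.18802 + 0.84162 × 0.18800)² / 0.004² = 17,341 (table 17,307)
- 90%: (1.95996 × 0.18802 + 1.28155 × 0.18800)² / 0.004² = 23,215 (table 23,170)

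At 3%: p2 = 0.024, p̄ = 0.027, and the two square roots are 0.22922 and 0.22918.

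- 80%: (1.95996 × 0.22922 + 0.84162 × 0.22918)² / 0.006² = 11,455 (table 11,433)
- 90%: (1.95996 × 0.22922 + 1.28155 × 0.22918)² / 0.006² = 15,334 (table 15,305)

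The same formula reproduces all 56 entries of the two tables to within 0.7%. The tables are therefore sound, and two-sided alpha is the reading that generates them.

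**Power at the sizes named in the protocol**

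Solving the formula for power: power = Φ{ [|p1 − p2|·√n − z(1−α/2)·√(2p̄(1−p̄))] / √(p1(1−p1) + p2(1−p2)) }.

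| n per group | Source | Power at 2% | Power at 3% |
|---|---|---|---|
| 17,307 | 8.5, for 2% | 79.9% | – |
| 11,433 | 8.5, for 3% | – | 79.9% |
| 11,000 | abstract minimum | 60.7% | 78.4% |
| 24,000 | apixaban cohort assumed in 8.5 | 90.9% | 98.2% |

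For example, 11,000 at 2%: (0.004 × 104.88 − 0.36851) / 0.18800 = 0.271, and Φ(0.271) = 0.607.

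**Other readings of the 90% claim**

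- One-sided alpha 0.05: 87.6% at both quoted sizes. 90% would need 18,920 and 12,498.
- Two-sided alpha 0.025: 71.1% at both.
- Continuity correction: 90% would need 23,712 and 15,666.
- Schoenfeld's formula on expected events: 17,307 × 0.02 × 1.8 = 623 events gives 79.5%, and 11,433 × 0.03 × 1.8 = 617 events gives 79.2%.

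None of these gives 90% at 17,307 or 11,433.

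**Which planning risk fits the protocol's own event counts**

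Section 8.5 expects 300–400 major bleeds in the first year among 24,000 apixaban users, or 1.25–1.67%, and cites 90 among about 6,000, or 1.5%. A relative risk of 0.8 on a 2% background gives 1.6% (384 in 24,000). On a 3% background it gives 2.4% (576 in 24,000). The counts sit nearer the 2% case, where 11,000 gives 60.7%. They refer to major bleeding, while the primary endpoint is any bleeding at an acute overnight hospitalization, so this is an indication only.

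**The case against.** Four points can be made for the protocol.

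- **The expected cohort is larger.** Section 8.5 assumes 24,000 apixaban users and calls this conservative. That exceeds the correct 90% sizes at both risks. If they are kept one-to-one after matching, the study has about 91% power at 2% and 98% at 3%. This stands: the error does not show that the study is underpowered. It does not make the two sentences true, however, and the margin at 2% is only 830 users (24,000 − 23,170) before any are lost in matching.
- **The warfarin group may be larger.** The protocol states no matching ratio. With two warfarin users per apixaban user, the quoted sizes would give 89.6%, and 11,000 would give 72.3% (2%) or 88.4% (3%). With three, the quoted sizes would give 92.7%, and 11,000 would give 77.1% or 91.8%. The figures for 11,000 are therefore conditional on equal groups. But the text cites tables of equal group sizes as the source of its 90%, and those tables say 80%.
- **At 3% the minimum is near enough.** 11,000 looks like 11,433 rounded down and costs only 1.6 points against 80%. That is fair. The material shortfall is at 2%, or against the 90% in the text.
- **Nothing turns on it.** The study takes all eligible initiators, reports hazard ratios with 95% confidence intervals, and marks hypothesis testing as not applicable in its ENCePP checklist. Interval widths will show the precision achieved. This limits the harm, but the protocol still states a wrong power for a primary endpoint.

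**Conclusion.** The concern holds. At relative risk 0.8 and alpha 0.05, the sizes 17,307 (2% risk) and 11,433 (3% risk) carry 80% power, not the 90% stated. 90% needs 23,170 and 15,305. This part rests on nothing beyond the protocol's own tables, and recalculation confirms them.

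The abstract's minimum of 11,000 lies below both 80% sizes. With equal matched groups it gives 78.4% at 3% and 60.7% at 2%, or type II errors of about 22% and 39%. That part rests on one-to-one groups, as the tables assume, and on all 11,000 being kept after matching.

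The defect lies in the stated justification and the committed minimum. Power actually achieved depends on the cohort found and on matching, and may well be adequate.

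**What to change.** 1. In 8.5, either keep 17,307 and 11,433 and state 80% power, or keep 90% and state 23,170 (2%) and 15,305 (3%).
2. In the abstract, either replace 11,000 with the table figure chosen, or state what it delivers: 78% power at 3% risk and 61% at 2%, for relative risk 0.8 at two-sided alpha 0.05 with equal groups.
3. Say that these are sizes per group after matching, which is what the tables' per-group numbers mean for a propensity-score matched analysis, and not counts of patients dispensed apixaban. If the matching is not one-to-one, recompute for the ratio used.

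The cost is two sentences in 8.5 and one in the abstract, with no new patients, data or analyses. The stated power, or the stated size requirement, becomes less favourable.

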8.1. Study design

This study will be a cohort study based on data from national routine population-based administrative health registries and databases in Denmark, Norway, and Sweden. The period

for identifying the study population (identification period) will be from 01 January 2013 to 31 December 2016, to reflect dates of apixaban availability and the years of available data. For each patient included in the study, the date of dispensing of the first OAC during the above period will be the index date (Figure 1).

This study will utilize the ‘active comparator new user’ design (34-36). Restriction of the study population to OAC treatment initiators (new users) emulates the principle of RCTs of aligning the start of follow-up with the start of treatment. This design reduces the risk of selection bias, such as healthy initiator bias, whereby prevalent users of medications may represent a selected group of all users, in that they are depleted of patients who discontinued treatment after experiencing an adverse event (AE) shortly after initiation (‘depletion of susceptibles’) (37). Depletion of susceptibles is avoided by the new user design. Propensity-score matched contrasts will be estimated for each NOAC vs. warfarin, to allow comparison of results with those from RCTs.

Figure 1. Study design schema

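### The study-size figures count all apixaban users, but the adjusted analysis uses matched samples, so on the tables' equal-group basis the stated minimums are too low

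*Protocol*

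**What the plan says.** Section 8.5 of the protocol presents Tables 3 and 4 as the "per-group size needed to detect a given increase/reduction of 1-year bleeding risk for alpha = 0.025 and alpha = 0.05", with "calculations performed using PROC POWER in SAS 9.4". On the risk assumption it says: "The 1-year background risk of bleeding was set to 2% in Table 3, and 3% in Table 4". Each row gives a single N per group, so both tables describe two groups of equal size.

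The text of 8.5 then turns a table entry into a condition on the cohort. The study "should be able to identify a relative risk (RR) of 0.8 with a power of 90% and an alpha of 0.05" at 2% risk "if there are included at least 17,307 apixaban users (the smallest group"; the matching figure at 3% risk is 11,433 apixaban users. The abstract states the minimum in the same unit: "The study will include at least 11,000 patients who were dispensed apixaban for the first time during the study period".

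The comparative estimates are planned on a different set. The abstract says "Adjusted estimates will be obtained using NOAC-warfarin pairwise propensity-score matched samples", and section 8.1 says "Propensity-score matched contrasts will be estimated for each NOAC vs. warfarin, to allow comparison of results with those from RCTs". An adjusted analysis of the full, unmatched dataset appears only among the sensitivity analyses in 8.7.3. Section 8.5 also works with an assumed apixaban cohort of 24,000. It gives no match fraction, no matching ratio and no allowance for unmatched users.

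**The concern.** The N in a two-group power table is the number analysed in each group. In a matched analysis that is the number of apixaban users who are matched, not the number who started the drug. Section 8.5 and the abstract use the second count where the tables supply the first. Unless every user is matched, the analysed group is smaller than the figure that was checked against the table.

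A cohort that only just reached a stated minimum would then be described as large enough, while the matched comparison behind the primary objectives had less power than the table row shows. A matched bleeding hazard ratio near 1 could be given more weight than the data support. The rivaroxaban and dabigatran contrasts raise the same issue, because each has its own matched sample.

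**Working it through.** **Inputs from protocol section 8.5:** relative risk 0.8; alpha 0.05; yearly risk p1 = 0.02 or 0.03, so p2 = 0.8 × p1; equal groups; assumed apixaban cohort 24,000.

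**Inputs not in the document:** the match fraction m, taken here as 80-100%, and the matching ratio, taken as 1:1 because the tables use equal groups. A 1:2 ratio is shown for contrast. Two-sided testing is also unstated, but it is what reproduces the tables.

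**Step 1. Reproduce the tables.** Two-sided test of two proportions, pooled variance under the null, with p̄ = (p1 + p2)/2:

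n = [1.960 √(2p̄(1−p̄)) + z_power √(p1(1−p1) + p2(1−p2))]² / (p1 − p2)²

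For 2% risk and 80% power: [1.960 × 0.18802 + 0.8416 × 0.18800]² / 0.004² = 17,341, against 17,307 in Table 3.

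| Risk | Power | Recomputed | Protocol table |
|---|---|---|---|
| 2% | 80% | 17,341 | 17,307 |
| 2% | 90% | 23,215 | 23,170 |
| 3% | 80% | 11,455 | 11,433 |
| 3% | 90% | 15,334 | 15,305 |

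All agree to within 0.3%. A likelihood-ratio form of the test agrees to within 1 per group. A one-sided alpha of 0.05 gives 13,660 and 9,023 at 80% power and does not reproduce the tables. So 17,307 and 11,433 are the 80%-power rows, although the sentence in 8.5 attaches 90% to them. That is a separate error, but it decides which row the fix must start from.

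**Step 2. Power when only a fraction m is matched (1:1).** Analysed n = m × users, and

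power = Φ( [|p1 − p2| √n − 1.960 √(2p̄(1−p̄))] / √(p1(1−p1) + p2(1−p2)) )

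For 17,307 users, 2% risk and m = 0.8: n = 13,846; (0.004 × 117.67 − 0.36852)/0.18800 = 0.543; Φ = 70.7%.

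| Users | Risk | All matched | 90% matched | 80% matched |
|---|---|---|---|---|
| 17,307 | 2% | 79.9% | 75.7% | 70.7% |
| 11,433 | 3% | 79.9% | 75.7% | 70.7% |
| 11,000 | 3% | 78.4% | 74.0% | 69.0% |
| 24,000 | 2% | 90.9% | 87.8% | 83.8% |
| 24,000 | 3% | 98.2% | 97.0% | 95.2% |

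**Step 3. Dependence on the ratio.** With two warfarin patients per apixaban user, 17,307 users (2%) or 11,433 (3%) give about 90% if all match, 86% at 90% matched and 82% at 80% matched.

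**Step 4. Room in the assumed cohort (1:1).** Lowest match fraction at which 24,000 users still supply the table N:
- 80% power: 17,307/24,000 = 72% (2% risk); 11,433/24,000 = 48% (3% risk).
- 90% power: 23,170/24,000 = 97% (2% risk); 15,305/24,000 = 64% (3% risk).

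**Step 5. Users needed before 1:1 matching, N/m.**

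| Power | Risk | Table N | 90% matched | 80% matched |
|---|---|---|---|---|
| 90% | 2% | 23,170 | 25,745 | 28,963 |
| 90% | 3% | 15,305 | 17,006 | 19,132 |
| 80% | 2% | 17,307 | 19,230 | 21,634 |
| 80% | 3% | 11,433 | 12,704 | 14,292 |

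**The case against.** **The protocol does not say that matching is 1:1.** In the abstract, pairwise describes the drug contrasts, not pairs of patients, and matching details may properly sit in the SAP. This stands. A reader might infer that the tabulated power holds only if every apixaban user is matched; that is true only at 1:1, and Step 3 shows it fails at 1:2. It does not rescue the text, though: if another ratio is planned, equal-group tables do not describe the planned analysis, and 8.5 needs restating for that reason instead.

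**The match fraction is the reviewer's assumption.** Also true. The direction of the effect at a fixed ratio does not depend on it; the size does.

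**The assumed cohort leaves room.** It does. A reader might infer that the study will be underpowered. The document does not support that: 8.5 assumes 24,000 users and calls this conservative, and at 80% matched 1:1 that still gives about 84% power at 2% risk and 95% at 3%. The room is thin only for the 90% claim at 2% risk, which needs about 97% matched.

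**No decision hangs on these numbers.** The ENCePP checklist marks hypotheses to be tested as not applicable, the results are hazard ratios with 95% intervals, and the interval will show the precision actually reached. This limits the harm. It does not make the stated minimum correct.

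**The wording could be read as meaning the analysed group.** The 8.5 sentence alone might be. The abstract's count of patients dispensed apixaban cannot be.

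**Conclusion.** The point holds in a limited form. Section 8.5 and the abstract attach an analysed-group N to apixaban users before matching and allow nothing for those left unmatched. No table entry is miscalculated on this account; the entries are applied to the wrong count.

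On the tables' 1:1 basis, the loss at the stated sizes of 17,307 and 11,433 is about 4 percentage points of power if 90% are matched and about 9 if 80% are, starting from 80%. Both the ratio and the fraction are assumptions. The finding is that the stated minimums are too low on that basis. It says nothing against the adequacy of a 24,000-user cohort for 80% power, and it is smaller than the mismatch between the 90% claim and the 80% rows: moving from 17,307 to 23,170 adds 34% (23,170/17,307 = 1.34), whereas 80-90% matching adds 11-25% (1/0.9 to 1/0.8).

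**What to change.** In section 8.5 and the abstract:

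1. State the required N as matched NOAC users per contrast with warfarin.
2. State the assumed matching ratio and match fraction. If the ratio is not 1:1, recompute the tables for it.
3. Restate the minimum number of users as N divided by the match fraction, starting from the table row for the power actually claimed. With 1:1 matching and 80-90% matched, 90% power needs about 25,700-29,000 users at 2% risk or 17,000-19,100 at 3%. If the claim is restated as 80% power, the figures are about 19,200-21,600 or 12,700-14,300.
4. Give the power at 24,000 users under the same assumptions: about 84-88% at 2% risk and 95-97% at 3%.

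The cost is a few sentences and figures. No recruitment is added, because the cohort comes from registries. The stated minimum rises, or the stated power falls somewhat.
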